## Protocol Synopsis

### *Brief Summary*

We will conduct a parallel-arm, double-blind individually randomized control trial (RCT) in 30 healthy older adults, where attentional control demands in working memory training will be systematically increased using engaging game-based simulations. There are three parallel arms. The first two arms use experimenter-designed simulation games, where participants will be trained on either predictable low attentional control (Arm 1: Low-C) or unpredictable high attentional control (Arm 2: High-C) working memory games. The third arm uses a commercially-available strategy video game requiring highest level of attentional control (Arm 3: High-C+), by adding multi-tasking to the unpredictable attentional shifts in working memory. In all three training arms, neural and cognitive changes in both near and far tasks will be examined immediately after the 8-week long intervention. Long-term cognitive changes will also be assessed at 6 months after completion of training. The far and near cognitive domains that will be examined in this RCT are episodic memory (the primary cognitive outcome, and a marker of early stages of AD) and executive control (the secondary cognitive outcome). We expect that the high attentional control training arms will greatly improve both primary and secondary cognitive outcomes in older adults not only immediately after the training, but also at the +6-month period. We also expect cognitive frailty to interact with the extent to which attentional control is trained.

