Additionally, a single-session, baseline functional neuroimaging data-set will be collected in a control group of 18 younger adults. These younger adults will not undergo any training. High attentional control training arms (High-C and High-C+) are also expected to heighten compensatory brain activation in older adults after intervention, for both episodic memory (primary outcome) and executive control (secondary outcome) in-scanner tasks, paralleling the baseline activity of younger brains. These high attentional control training arms are also expected to positively impact brain structures that progressively decline with aging. The data from younger adults, our functional control group, will provide critical information about the brain regions activated in young, healthy brains during episodic memory (far transfer) and executive functions (near transfer). It will also help us determine whether older adults' brain activity following training resembles that of younger brains.

The primary objectives of this double-blind RCT are to evaluate the efficacy of high attentional control training on episodic memory (primary cognitive outcome) in an older adult population, by evaluating a) immediate training-related

changes in performance and neural activation during episodic memory tasks, and b) long-term changes at a +6-month retention period in performance during episodic memory tasks. The secondary objective of this RCT is to evaluate the efficacy of high attentional control training on executive functions (secondary cognitive outcome) in an older adult population by evaluating neuro-cognitive changes in executive functions immediately after the training, and cognitive gains at +6-month retention period.

In order to achieve these objectives, cognitive measures of both primary and secondary outcomes will be collected in healthy older adults at before training (baseline), immediately after 8 weeks of training (immediate post-training), and 6 months after training completion. MRI scanning, including fMRI tasks of episodic memory (primary outcome) and executive functions (secondary outcome), will be conducted at baseline and at immediate post-training for older adults, and only once in younger adults.

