### ***Study timeline for Year 1***

The first quarter of year 1 (that is, 0-3 months after the notice of the award) will include a study preparation phase, where we will finalize the study protocol, acquire and set-up the testing computers, tablets and licensed neurocognitive tests, advertise to recruit young and old participants, hire required personnel, and test the final versions of the games and the neurocognitive computerized tasks on the newly acquired computers and set up data safety protocols. In addition, data collection on 25 younger adults (the functional control group) and 26 older adults (10 Low-C; 10 High-C; 6 High-C+) will be completed within during this first year. This will provide us with some pilot data by the end of year 1 to establish that the clinical trial can be successfully conducted, and identify age-related differences in brain functions during the near and far transfer tasks by comparing baseline fMRI data of older adults to that of younger adults.

Recruitment and enrollment of older adults for the clinical trial will begin in the third quarter of year 1 (that is, 6 months after notice of the award), after the clinical trial has been registered with [clinicaltrials.gov](https://clinicaltrials.gov).

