### **Study Design**

**Overview.** This parallel arm, individually randomized control trial (RCT) will recruit 34 older adults from Dallas and neighboring counties. We aim to retain at least 30 participants on whom immediate post-training gains in both *near* and *far* abilities can be observed. This RCT shall be registered at [ClinicalTrials.gov](https://clinicaltrials.gov). There will be a Clinical Coordination Team (co-directed by [name] and the Project Manager) that will implement the intervention and check in with the participants on a weekly basis regarding their training progress. A blinded data collection team, directed by a post-doctoral fellow, will collect both behavioral and neuroimaging assessments before and after training. There will also be

a Data Coordination Team (co-directed by [name] and a post-doctoral fellow) that will be responsible for scoring and preprocessing the data. All data will be deposited in a HIPAA compliant server at the PI's laboratory. The team leaders will meet twice a month and each team will meet weekly to oversee any issues with subject recruitment, logistics and data collection. We will also recruit a total of 20 younger adults (YA, 18-30 years of age) for neuroimaging, who will be the functional controls for the older adults in the RCT.

This is a Phase 1 trial with multiple interventions in older adults, where the goal is to compare high attentional control trainings (High-C and High-C+) to low attentional control training (Low-C) and evaluate training-related changes in neurocognitive functions of both near (secondary outcome) and far transfer (primary outcome) tasks.

***Experimental Design.*** There are three intervention arms for older adults (OA) in this RCT trial, where attentional control demands in working memory training will be systematically increased using engaging game-based simulations.

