clusters from YA will be used to extract percent signal change for all older individuals (OA) at both assessments. A univariate ANOVA with 3 groups (post-test Low-C, post-test High-C+, and YA) will be conducted to evaluate whether the post-test activations in High-C+ older adults in these task-related regions are closest to that of YA. We predict that for the primary (subsequent memory) and secondary (task-switching) outcomes, High-C and High-C+ older adults at post-training will have increased task-related neural activations mimicking that of younger adults, and reduced non-compensatory over-activations compared to baseline.

For the network analyses, we will utilize seed-to-voxel based connectivity from the major nodes within two cognitive networks, Fronto-Parietal (FP) and Cingulo-Opercular (CO), at both pre- and post-testing sessions. Changes in post-training functional connectivity in these two networks will be evaluated at all task difficulty conditions for memory updating (0-back, 3-back), task switching (single task, dual task), and subsequent memory task (water present, water absent). The interaction effects will help evaluate whether the connectivity of attentional networks change most for the higher attentional control training groups. We will also conduct separate pair-wise comparisons between High-C and High-C+ for both primary (*Subsequent Memory*) and secondary (*Task Switching*) cognitive outcomes, corrected for multiple comparisons, to determine if High-C+ engenders most neural changes.

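### A three-group ANOVA cannot show which training arm is closest to younger adults, and the plan gives no other rule for judging closeness or resemblance

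*Combined protocol and SAP*

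**What the plan says.** The Brief Summary gives the younger adults a specific purpose: their data should help show whether older adults' "brain activity following training resembles that of younger brains". The analysis meant to deliver this is in the Data Analysis Plan, under the neuroimaging outcomes. Regions are defined from YA activation, signal change in them is extracted for the older adults, and the two older arms, Low-C and High-C+ at post-test, are set against YA in a single univariate ANOVA, which "will be conducted to evaluate whether the post-test activations in High-C+ older adults in these task-related regions are closest to that of YA". The prediction that follows is that "High-C and High-C+ older adults at post-training will have increased task-related neural activations mimicking that of younger adults", although High-C is not one of the three groups in that ANOVA.

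On size, the Brief Summary describes an "individually randomized control trial (RCT) in 30 healthy older adults" and a "control group of 18 younger adults". Study Design says "We will also recruit a total of 20 younger adults", and the Year 1 timeline gives 25.

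Nothing further is specified for this ANOVA: no contrast involving YA, no measure of distance, no equivalence margin, no decision rule and no power.

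**The concern.** The null hypothesis of the F test is that three means are equal. 'Closest' is a statement about two distances, High-C+ to YA and Low-C to YA, and the F test does not compare them. F can be significant because both older arms sit equally far from YA. If F, or a High-C+ versus YA comparison, is not significant, the data are compatible with no difference but also with a sizeable one.

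At stake is the claim that training makes older brains look younger. It is a stated reason for scanning the YA group, and it concerns the fMRI measures listed as primary and secondary under Outcome Measures. With no rule fixed in advance, the reading would be chosen after the data are seen, and the nominal 5% level would not apply to the word 'closest'.

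**Working it through.** **The plan's own figure.** There is none for this analysis. The stated power (above 93% for 144 older adults at f = .16) concerns the arm-by-assessment interaction on the primary cognitive outcome. It reproduces: with an assumed correlation of 0.5, λ = N·m·f²/(1 − ρ) = 144 × 2 × 0.0256 / 0.5 = 14.7, which gives 93.5%. It does not bear on the YA comparison.

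**Inputs.** 30 older adults and 18 YA (Brief Summary). Assumed: equal split (10 per arm), common SD, two-sided 5%, one region.

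**Step 1: non-significance as evidence of resemblance.** The standard error of High-C+ minus YA in SD units is √(1/10 + 1/18) = 0.394, and the critical t on 26 df is 2.056.
- True gap 0.5 SD: 0.5/0.394 = 1.27; power 23%, so non-significant in 77% of trials.
- True gap 0.8 SD: 0.8/0.394 = 2.03; power 50%, so non-significant in 50%.
- 95% interval half-width: 2.056 × 0.394 = 0.81 SD.

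With 25 YA the non-significant shares are 75% and 45%, and the half-width is 0.76 SD.

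**Step 2: a significant F as evidence of 'closest'.** Both arms are simulated at the same true distance below YA, so neither is closer. Among trials with a significant F, High-C+ has the nearer sample mean in 50%, a coin toss. The share of trials in which High-C+ is called closest depends on the rule:

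| True gap, both arms | Significant F, Low-C differs from YA, High-C+ does not | Same pattern, no F required | Significant F and High-C+ mean nearer |
|---|---|---|---|
| 0.5 SD | 7% | 14% | 12% |
| 0.8 SD | 11% | 18% | 27% |
| 1.0 SD | 11% | 16% | 38% |

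At 0.8 SD the row becomes 12%, 19%, 29% with 20 YA and 14%, 20%, 32% with 25 YA. In the same equal-gap settings, a direct two-sided 5% test of High-C+ against Low-C errs in that direction 2.5% of the time.

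**Step 3: would a signed High-C+ minus Low-C contrast be enough?** Put Low-C 0.4 SD below YA and High-C+ 0.8 SD above, twice as far. The contrast is significantly positive in 74% of trials, so it would certify the farther arm as closer. Overshoot is plausible here, because the plan expects training to raise activation and itself discusses over-activation.

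**Step 4: what a formal resemblance claim would need.** With High-C+ truly equal to YA, the 95% interval lies within an illustrative 0.8 SD margin in about 8% of trials, and within 1.0 SD in about 39%.

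**The case against.** The strongest reply is that the rules in Step 2 are not the plan's. A reader might infer that the sponsor will treat 'Low-C differs from YA, High-C+ does not' as proof of 'closest', or a null result as proof of resemblance. The documents say neither. This stands: the documented fault is a test that does not match its question, with no rule to bridge the gap, and the percentages are illustrations.

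A reader might also infer that the claim always becomes easier as groups get smaller and noisier. That is not general. With equal true gaps of 0.5 SD, the pattern without the F falls from 14% at 10 per arm to 12% at 5 per arm; at 0.8 SD it hardly changes.

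It can further be said that the fMRI plan already tests the arms against each other. It does, through the arm-by-assessment ANOVA with its planned comparisons, post-test group differences, and High-C versus High-C+ comparisons. But none of these includes YA or is tied to distance from YA. If follow-ups against YA are implied, ordinary pairwise tests would produce the patterns tabulated above.

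Finally, this is a supplementary comparison with a non-randomized group in a small first-phase study. That limits the seriousness of the point but does not make the test fit the question.

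**Conclusion.** The point holds as a mismatch between test and question. The ANOVA cannot establish that High-C+ is closest to YA, and its non-significance cannot establish resemblance. That follows from the null hypothesis and needs no assumption about sample size.

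The size is illustrative. With both arms truly 0.8 SD from YA, a false 'closest' arises in about 11% to 27% of trials depending on the rule adopted, and a real 0.8 SD gap between High-C+ and YA goes undetected about half the time. These figures rest on 10 per arm, 18 YA, a common SD, a 5% level and a single region. The conclusion is the same with 20 or 25 YA.

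This should be corrected before analysis. It does not affect the arm-by-assessment tests that carry the randomized comparison.

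**What to change.** In the neuroimaging section of the Data Analysis Plan:

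1. Replace the ANOVA as the test of 'closest' with the estimate |Low-C − YA| minus |High-C+ − YA| in each YA-defined region, with a 95% interval (for example a bootstrap that resamples within all three groups). Claim that High-C+ is closer only if the interval excludes 0 in its favour. Do not rely on a signed High-C+ minus Low-C contrast alone, because it favours an arm that overshoots YA.
2. Report High-C+ minus YA with its 95% interval as descriptive.
3. State that a non-significant difference from YA will not be read as resemblance.
4. Reconcile the YA count (18, 20 or 25). Since the prediction also covers High-C, the same estimate can be given for that arm.

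The work is wording and a few lines of code on data already planned. The real cost is that 'closer' becomes harder to claim. If High-C+ equals YA and Low-C is 0.8 SD away, the significant/non-significant pattern would succeed in 48% of trials (37% if a significant F is required first) and a signed contrast in 41%. The distance estimate will do less well than the signed contrast: even at a true distance of zero, the expected sample distance of High-C+ from YA is 0.394 × √(2/π) ≈ 0.31 SD, which shrinks the estimated advantage. A formal 'resembles' claim is largely unattainable at this size (Step 4), hence the descriptive label. The change also leaves one limitation in place: regions chosen from YA activation are likely to overstate the YA mean, which distorts both distances.

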## Outcome Measures

### *Name:*

1. Episodic Memory: Cognitive
2. Episodic Memory: fMRI
3. Executive Functions: Cognitive
4. Executive Functions: fMRI
5. Reasoning
6. Working Memory Capacity
7. Psychosocial Well-being
8. Diffusion Tensor Imaging

**Primary Outcome:** Episodic Memory: Cognitive; Episodic Memory: fMRI

**Secondary Outcome:** Executive Functions: Cognitive; Executive Functions: fMRI

**Other:** Reasoning, Working Memory Capacity, Psychosocial Well-being, Diffusion Tensor Imaging

**Time Frame.** All behavioral and cognitive measures (episodic memory, Executive functions, reasoning, working memory and psycho-social well-being) will be collected at the following three time points: Baseline (Assessment A), Immediate Post-training (Assessment B), and Retention (Assessment C).

Neuroimaging measures, including DTI and the fMRI tasks of episodic memory and executive functions will be collected at only two time points: Baseline (Assessment A) and Immediate Post-training (Assessment B).

Episodic memory (Cognitive) will be characterized by a single score that will be obtained by averaging standardized scores of 4 episodic memory tasks, including a task of everyday memory. These tasks are *Picture Sequence Memory task* (from NIH toolbox), *Buschke's Selective Reminding Test*, *Story Recall* (from expanded MMSE) and *Rivermead Behavioral Memory Test* (a test of everyday memory).

Episodic memory (fMRI) will be characterized by BOLD activations in an event related *subsequent memory* fMRI task. Scanning will take place during encoding of 96 color photographs of outdoor scenes (4 s duration) interspersed with baseline trials of a fixation cross (of 4-16 s). During encoding, the participant will determine if water is present in the scene with a keypress. Twenty minutes after the scan, the participant will undergo a recognition judgement task along with confidence ratings of their responses, assessing their subsequent memory of scenes presented in the scanner. In this episodic memory task, the following contrasts will be assessed for each subject for both "water present"

(easy condition) and “water absent” (hard condition) scenes: Forgotten>Remembered items and Remembered>Forgotten items.

Executive Functions (Cognitive) will be characterized by a single score will be obtained by averaging the standardized scores of 6 tasks of executive functions, with 2 tasks for each subcomponent of executive function, namely, task-switching, inhibition and updating. The tasks are *Stroop* (Eprime) and *Dimensional Change Card Sort* (NIH Toolbox) for task switching; *Flanker* (NIH Toolbox) and *Cued-discrimination* for inhibitory control; *Visual n-back* and *Verbal n-back* for memory updating.

This will be characterized by BOLD activations in two fMRI tasks. 1) A hybrid event-related task-switching paradigm with 2 single and 2 dual task blocks (TR=2 s). In one single block, the participant will decide if the digit presented is odd or even; in other, s/he will decide if the digit presented <5 or >5. Digit 5 won't be used. In dual blocks, the two tasks will be randomly intermixed. Neural activity for the following three contrasts will be assessed for each subject: Single>Fix, Dual>Fix, and Dual>Single. 2) n-back memory updating task (TR=2 s, 2 runs of 4 task and 5 fixation blocks). During the task block, digits will be presented in the center of the screen. In 0-back blocks, s/he will just make a perceptual decision about the digit color. In 3-back blocks, s/he will compare the identity of the current digit with the digit presented 3-positions before. Neural activity for the following contrasts will be assessed for each subject: 3-back>Fix, 0-back>Fix and 3-back>0-back.

[figure not shown]
Reasoning will be characterized by a single score will be obtained by averaging the standardized scores of *Visual Puzzles* and *Matrix Reasoning* from WAIS-IV.

Working Memory Capacity will be characterized by a single score will be obtained by averaging the standardized scores of *List Sorting Working Memory Test* (NIH Toolbox) and *Operation Span* (Eprime).

Psychosocial well-being will be characterized by a single score will be obtained by averaging the standardized scores of *Geriatric Depression Scale*, *MIDUS-II*, *Cognitive Reserve Index*, and *Self-efficacy Scale*.

A 31-directions Diffusion Tensor Imaging (DTI; TR = 4001 ms, TE = 108 ms, FOV = 216 mm, voxel = 1.8 mm^3) or multi-band Diffusion Weighted Imaging (DWI), acquired in pairs of opposite phase encoding directions (RL and LR with 90 directions and a b-value of 2000 s/mm^2, and RL and LR with 91 directions and a b-value of 1000 s/mm^2) will be obtained. DTI will be characterized by fractional anisotropy (FA) and mean diffusivity (MD). Fractional anisotropy (FA) and mean diffusivity (MD) maps will be derived from tract-based spatial statistics, and regional values will be derived using the JHU atlas

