Arm 1: Low Attentional Control Group (Low-C). Low attentional control training using an n-back simulation game (*Birdwatch*), requiring predictable shifts of cued-attention. Arm 2: High Attentional Control Group (High-C). High attentional control training using the *Birdwatch* simulation game, requiring unpredictable shifts of cued-attention. Arm 3: Highest Attentional Control Group (High-C+). This arm uses a commercial strategy video game for training (*Sushi Chef*), rather than the experimenter-developed simulation games proposed in the other two arms. Additionally, a *comparison group of younger adults (YA)* will undergo pre-screening, mock scan, and MRI scan sessions (but no training). All older participants will undergo 3 behavioral assessment sessions, each lasting a maximum of 3.5 hours, in the PI's lab. These assessments will be conducted at baseline, immediately post-training and 6 months after completion of training. All older adults will also undergo 2 neuroimaging assessments, one at baseline, and another at immediate post-training. There will no more than 5-day difference between the MRI scan and the respective behavioral assessment at either baseline or at immediate post-training.

The training period will last for 19 h over 8 weeks, and will include both in-lab and at-home training on a device provided to the participant. All training will be administered individually to the participant, not in a group. Fig. 5 and Fig. 6 show the computerized games used in the three training arms.

***Screening and Randomization.*** In this individually randomized trial, all interested participants will first be prescreened and will undergo a Mock Scan session to determine their eligibility to participate in the study. Participants will be consented to screening for eligibility. In order to exclude participants with memory-related disorders, primarily MCI and AD, participants will be required to have both a Mini-mental Status Examination (MMSE) score of 26 or greater, and a

Montreal Cognitive Assessment (MoCA) score of 24 or greater. A composite of these two standardized scores will comprise an index of *cognitive frailty*. The cutoff scores are conservative and should screen out most cases of MCI, although we acknowledge that some early stage MCI individuals could still be included. Additionally, brain scans will be screened by a neuroradiologist if a pathology is suspected.

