***Analyses of Primary and Secondary Neuroimaging Outcomes.*** There are two main fMRI tasks of interest- one for primary cognitive outcome (episodic memory), called *subsequent memory*; another for secondary cognitive outcome (executive control), called *task-switching*. An additional fMRI task, *working memory updating*, a near transfer task for all arms, will also be evaluated. For each task, we will derive a summary BOLD measure that best characterizes neural activity for the task after correcting for multiple comparisons. Those summary values will be entered into an ANOVA, where the Training Arm (3: Low-C, High-C, High-C+) x Assessment (pre-test vs. post-test) interaction will be evaluated, followed by post-hoc analyses of these interaction effects. We will also calculate group differences in the contrasts of interest at the post-test scans. The critical contrasts of interest for the subsequent memory is Remembered vs. Forgotten items, and for task-switching is Dual vs. Single task. The resulting ROI clusters, after correcting for multiple comparisons, will be used to extract percent signal change for all individuals at both pre-test and post-test. Specific Aim 2 evaluates whether the post-training changes in fronto-parietal activations are largest in the High-C and High-C+, compared to the Low-C, training arms. The percent signal change data will be submitted to a Training Arm x Assessment ANOVA, which will be followed by planned-comparisons between the groups to evaluate the specific aim 2. These interaction effects will be conducted for all task difficulty conditions in the fMRI tasks, because post-intervention activation patterns are hypothesized to be different for simpler conditions (e.g., 0-back; Single task; water present) compared to the more difficult conditions (e.g., 3- back, Dual task; water absent) of the fMRI tasks. We will also calculate task-specific activations for difficult vs. simpler condition contrasts (e.g., 3-back>0-back; Dual>Single; water absent>water present) in younger adults (YA), after correcting for multiple comparisons. The resulting ROI

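### One third of the executive-function composite is n-back, the paradigm trained in the two Birdwatch arms but not in High-C+, so contrasts with High-C+ mix task practice with transfer

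*Combined protocol and SAP*

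**What the plan says.** Under Outcome Measures, the executive-function score is obtained by "averaging the standardized scores of 6 tasks of executive functions, with 2 tasks for each subcomponent of executive function". The updating subcomponent is "Visual n-back* and *Verbal n-back* for memory updating" and nothing else.

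Under Study Design (Experimental Design), the arms train as follows:
- Low-C: "Low attentional control training using an n-back simulation game (*Birdwatch*), requiring predictable shifts of cued-attention".
- High-C: "High attentional control training using the *Birdwatch* simulation game, requiring unpredictable shifts of cued-attention".
- High-C+: "This arm uses a commercial strategy video game for training (*Sushi Chef*), rather than the experimenter-developed simulation games proposed in the other two arms". The Brief Summary says this arm raises the demand "by adding multi-tasking to the unpredictable attentional shifts in working memory".

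The Data Analysis Plan enters one composite per outcome into the Training Arm x Assessment ANOVA, tested at .025, and names pairwise contrasts between High-C and High-C+. It repeats this for the secondary outcome. It plans no cognitive analysis by subcomponent or without the n-back tests. In the neuroimaging part of that plan, the fMRI updating task is called "a near transfer task for all arms, will also be evaluated".

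**The concern.** For participants who train on Birdwatch, the two n-back tests are close to the trained task. For High-C+ participants they are a new task. A plain average of six tasks cannot show whether a difference between High-C+ and another arm reflects practice on one paradigm or wider executive transfer.

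The one pairwise cognitive contrast that the plan names, High-C versus High-C+, falls on this asymmetry. So does High-C+ versus Low-C, which is part of the trial's stated goal. A High-C advantage on the composite could come from n-back practice alone. A true High-C+ advantage on the other tasks could be partly hidden.

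**Working it through.** **Inputs from the document.** Six equally weighted tasks, two of them n-back. Planning f = .16 for the Arm x Assessment interaction. Total N = 144 at immediate post-training in the full trial, about 30 retained in this study. Alpha .025 per ANOVA.

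**Assumed, not in the document.** The extra n-back gain from Birdwatch practice, b = 0.2, 0.5 or 0.8 SD per test. Inter-task correlation r = .3 (.2 to .5 as a check). Pre-post correlation .5.

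**Step 1: the scale of the planning f.** Noncentrality = f² x N x 2/(1 - .5), with 2 and N - 3 degrees of freedom. For N = 144 and f = .16 this is .0256 x 144 x 4 = 14.7, which gives 93.5% power at .05 (stated: above 93%). N = 117 gives 87.4% (stated: above 87%). The plan's figures reproduce, so .16 is an interaction f on this scale.

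**Step 2: shift in the composite.** Weight of n-back = 2/6, so shift = b/3. The composite SD is √((1 + 5r)/6) = √(2.5/6) = 0.645 at r = .3.

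**Step 3: convert to f.** With gains (s, s, 0) in Low-C, High-C and High-C+, the SD of the three arm means is s√2/3. That gives a between-arm f at post-test only. In the interaction the difference is spread over two assessments, so each cell effect is half as large: interaction f = (s/SD) x √2/6.

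| b | Shift (units) | Shift (composite SD) | Post-test between-arm f | Interaction f | Significant at .025, N = 144 | Same, N = 30 |
|---|---|---|---|---|---|---|
| 0.2 | 0.07 | 0.10 | .05 | .02 | 4% | 3% |
| 0.5 | 0.17 | 0.26 | .12 | .06 | 16% | 4% |
| 0.8 | 0.27 | 0.41 | .19 | .10 | 42% | 8% |

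The last two columns suppose no other difference between arms, so the nominal rate is 2.5%. Over r = .5 to .2, the interaction f runs from .051 to .068 for b = 0.5 and from .082 to .109 for b = 0.8.

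**Step 4: two reference values.** For this two-against-one pattern, f = .16 needs a difference of .16 x 6/√2 = 0.68 composite SD, against 0.10-0.41 here. To tie with High-C on the six-task mean, High-C+ would need an advantage t on each of the other four tasks with 4t/6 = 2b/6, so t = b/2 = 0.10, 0.25 or 0.40 SD.

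**The case against.** **Near transfer is the purpose of this outcome.** The plan treats executive function as the near-transfer domain and presents all three arms as working-memory training, so some overlap with training is intended. That stands for the construct. It does not remove the difference between arms in which test paradigm was practised. The phrase about all arms is said of the fMRI updating task and does not address the behavioural composite.

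**High-C is called n-back only by inference.** The word is used for Low-C. High-C uses the same game, and the Fig. 5 caption describes birds that must be left out of later comparisons, which fits. The figures are not available here, so how closely the game resembles the two tests cannot be judged.

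**Stronger readings that the document does not support:**
- A reader might infer that the whole composite is tilted against High-C+. The n-back third favours the Birdwatch arms if practice helps, but the multi-tasking in High-C+ could favour the two tests classed as task switching. The net direction is not known.
- A reader might set the post-test f of .12-.19 (b = 0.5-0.8) beside .16 and call the artefact as large as the planned effect. Those are different scales. Like for like it is about .06-.10.
- A reader might say that the tilt works against a predicted overall High-C+ advantage. For cognition, the plan predicts that the better of the two high-control arms depends on cognitive frailty, not that High-C+ wins overall.

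**Conclusion.** The structural point holds: one third of the secondary cognitive score is trained paradigm for two arms and untrained for the third, and no planned cognitive analysis separates the parts. It concerns contrasts of High-C+ with High-C or Low-C only. Episodic memory contains no n-back test. The n-back fMRI task listed under executive functions has the same overlap.

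The size depends on assumed practice gains and correlations. Over the range shown, the effect is smaller than the planning effect. With about 30 participants it would seldom change significance, so in this study the harm is a biased estimate of the High-C versus High-C+ difference. Because the study is presented as an early stage of a bigger trial, that estimate may carry forward. This is an inexpensive improvement to a secondary outcome, not a flaw in the primary analysis.

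**What to change.** Keep the six-task composite as the secondary outcome. Before unblinded analysis, pre-specify:
1. The same Arm x Assessment analysis and pairwise contrasts on the mean of the four tasks that are not n-back.
2. A separate report of the two-task n-back score by arm.
3. An interpretation rule. If a difference involving High-C+ appears in the six-task score, but its estimate shrinks to near zero or reverses in the four-task score, attribute it to the updating/n-back tasks and not to broader executive transfer.

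In the neuroimaging analysis section, qualify the near-transfer label to say that n-back is the trained paradigm for the Birdwatch arms.

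No new data are needed. The four-task score leaves out updating, a third of the construct, and is slightly less reliable. It should therefore guide interpretation, not replace the outcome or act as a significance gate.
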